3.5 Study Population

The Inhibitor Eradication Trial will enroll 90 adults and children \geq 4 months of age with severe hemophilia A with high-responding inhibitors (anti-FVIII \geq 5.0 BU) who are ITI-refractory or ITI-naïve, or developed on the Prevention Trial.

The Inclusion Criteria for the Eradicate Trial include children and adults \leq 4 months of age; severe hemophilia A (FVIII < 0.01 U/ml); current or past high-responding inhibitor to FVIII (anti-FVIII \geq 5.0 B.U.), or ITI-refractory or ITI-naive. Exclusion Criteria include acquired hemophilia or any bleeding disorder other than hemophilia A; use of an experimental drug(s); surgery anticipated in the next 48 weeks (except port placement); life expectancy less than 5 years; patient/parent/caretaker unable or unwilling to keep a personal diary of bleeding frequency and study drug treatment, make monthly visits and blood draws; or other illness, condition, or reason in the opinion of the investigator that would make the patient unsuitable for the trial.

Our 2019 survey indicates there are 274 refractory inhibitor patients at 31 HTCs. When combined with 12 inhibitor patients from the Prevention Trial (8x25% plus 52x15% = 12), that is 25% of N=8 Eloctate-treated and 15% of N=52 Emicizumab-treated, for a total 4+8=12, we will achieve 90 inhibitor subjects (78+12) over the 6-year enrollment. With *only* 29% participating, we will enroll 78 refractory inhibitor patients plus 12 inhibitor patients from the Prevention Trial, we will enroll 90 severe hemophilia A inhibitor subjects over the 6-year enrollment period (Table 1).

Inhibitors in 6 yr Prevention Trial	Non-Trial Inhibitors at HTC	% of 6 yr Total for 6 yr Trial	Sample Size, Power for 6 Yr Trial
N=12 (8 x 25% = 4) + (52 x 15% = 8)	N = 274 refractory/untreated	29% of 274 = ~78 in 6 yr	90 (78 + 12) Inhib: β=0.80, α=0.05

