Hypothesis 1: We hypothesize that Eloctate ITI q.o.d. plus weekly Emicizumab is superior to Eloctate ITI q.o.d. alone in eradicating inhibitors, anti-FVIII < 0.6 B.U. (CBA), when given for 48 weeks in children and adults with severe hemophilia A and high-responding inhibitors (historic anti-FVIII > 5.0 B.U.). Yet there is equipoise, as while Eloctate ITI may reduce the time to tolerance it is burdensome with qod dosing and data are available from small, nonrandomized studies. While both drugs may shorten ITI and even be synergistic, there is equipoise in the absence of randomized trials. While Emicizumab has been tried in hemophilia A inhibitor patients in small nonrandomized studies, there are no data on whether it reduces time to tolerance. As *Emicizumab* is given subcutaneously weekly, if, when given with *Eloctate ITI*, it was superior to *Eloctate* ITI alone in reducing time to ITI, it would be the "winner" over *Eloctate ITI alone*.

Specific Aim 2: To evaluate the safety and mechanism of inhibitor suppression *eradication* in patients with severe hemophilia A and inhibitors. Secondary endpoints include a) *safety,* measured by number and frequency of bleeding episodes (i.e. hematomas, hemarthroses) and associated factor use and port infections; and b) *mechanism of inhibitor suppression eradication,* measured by FVIII-specific T cell ELISPOT assay; FVIII genotype; HLA type; and chromogenic FVIII trough levels; and by micriobiome stool sample, each compared with anti-FVIII.

Hypothesis 2: We hypothesize that safety, measured by bleeds requiring rescue factor or prophylaxis escalation, and port infections, will not differ between treatment arms; and the mechanism by which *Eloctate* suppresses (prevents, eradicates) inhibitor formation is via Fc induction of regulatory T cells (Tregs) promoting FVIII tolerance, measured by ELISPOT assay. This novel approach to eradicate inhibitors is compelling, and, if successful, will reduce the burden of inhibitor formation and the associated morbidity, hospitalization, cost, and early mortality, and be adopted immediately into clinical practice.

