- Blood draw: A 3.8 ml (¾ tsp) blood sample will be collected for anti-FVIII chromogenic Nijmegen Bethesda (CBA) assay (plasma), antigen-specific (FVIII) T cell ELISPOT assay (PBMC), HLA and hemophilia genotype (buffy coat of the plasma sample), trough FVIII chromogenic activity (aliquot of plasma), and a sample (plasma) stored for future studies. All samples must be drawn prior to the study drug dose. Amounts of blood drawn will be less for children weighing less than 14 pounds. The Appendix detailing timing of visits and blood draws is attached at the end of this protocol.
- The samples (all de-identified) and labeled with subject ID number will be processed, frozen, and shipped to a repository in the Coagulation Laboratory at Vitalant, Pittsburgh PA, under the direction of [name]. The inhibitor titer will be run by chromogenic Nijmegen Bethesda (CBA) assay real time, with confirmation on stored aliquots for those testing negative (< 0.6 B.U.). An aliquot of plasma sample will be assessed for trough FVIII chromogenic assay (aliquot of plasma sample). The micriobiome (stool) sample will be shipped to the Vitalant Lab and transported to the microbiome, Vascular Medicine Institute (VMI), Pittsburgh, under the direction of [name]. The PBMC sample will be snap frozen in dimethyl sulfoxide (DMSO) and stored in liquid nitrogen until batch testing for antigen-specific (FVIII) T cell responses by ELISPOT assay in the research laboratory of [name], Uniformed Services of the Health Sciences (USUHS), Bethesda, MD. Samples for future testing (for hemophilia genotype or immunologic studies) will be stored indefinitely.

- Stool sample: A small stool sample will be collected at home to assess genes and bacteria in the gut (micriobiome) and placed in a small tube and returned in a container mailer to Vitalant, and couriered to VMI, Pittsburgh PA.
- After the study physician determines eligibility, the subject will be **randomly assigned to one of the two treatment strategies**, *Eloctate ITI* plus *Emicizumab* or *Eloctate ITI alone*.

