4.0 Human Subjects

4.1 General Characteristics - Minority Inclusion and Non-Discriminatory Statements

For the Inhibitor Eradication Trial, adults or children \geq 4 months of age with severe hemophilia A and a current or past high-responding inhibitor to FVIII, anti-FVIII \geq 5.0 B.U., are eligible to participate. Subjects will include those who develop inhibitors in the Prevention Trial or those who have been refractory or never tolerized at the same HTCs. As hemophilia is an X-linked congenital disorder, >98% of whom are male, it is anticipated that the study population will be male, and as almost 90% are Caucasian, it is anticipated that the majority of subjects will be Caucasian males. For the trial, subjects will be children or adults \geq 4 months of age with severe hemophilia A, FVIII < 0.01 IU/mI), with current or past high-responding inhibitor to FVIII, anti-FVIII \geq 5.0 B.U.

Currently there is no known effective approach to eradicate inhibitors, and they remain major complications of hemophilia. The trial will assess *Eloctate* ITI (tolerance induction) with or without *Emicizumab* to eradicate inhibitors, and rFVIIa will be used to treat bleeds. There will be no discrimination based on race or ethnicity (see Targeted/Planned Enrollment Table). The racial, gender and ethnic characteristics of the proposed subject population reflects the demographics of Pittsburgh, surrounding area, and the subject population of the University of Pittsburgh Medical Center. We shall attempt to recruit subjects in proportion to these demographics. All subjects will be screened prior to enrollment to confirm the diagnosis of severe hemophilia A, FVIII < 0.01 U/ml. Written, informed consent will be obtained from all subjects at the screening visit. Once eligibility is confirmed, visit 1 will be the start of enrollment. For the Eradicate Trial, 90 subjects (2-4 per site) will be enrolled.

4.2 Inclusion of Children:

The optimal approach to prevention and eradication of inhibitor formation in hemophilia is unknown. Among those

who develop inhibitors, 95% occur within 50 treatment exposures, usually in the first two years of life, but unless inhibitors are tolerized, they may last a lifetime, and thus affect children and adults of all age. Thus, the **Inhibitor Eradication Trial** is limited to male children or adults with severe hemophilia A and an inhibitor to factor VIII, anti-FVIII \geq 5.0 B.U.

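### Past inhibitors are admitted and no visible rule requires a positive baseline titre, so a subject with no inhibitor at entry can count as an eradication

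*Combined protocol and SAP*

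**What the plan says.** **Entry.** Section 3.5 lists a "current or past high-responding inhibitor to FVIII" of at least 5.0 B.U. Section 4.1 repeats it as "a current or past high-responding inhibitor to FVIII", and the protocol summary, abstract and sections 1.0, 3.2, 3.3 and 4.5 also pair current with past. Hypothesis 1 in section 2.1 speaks of "high-responding inhibitors (historic anti-FVIII > 5.0 B.U". No exclusion in section 3.5 or 4.3 concerns a negative current titre.

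**Baseline titre.** Section 3.2 has a CBA titre drawn at the screening/baseline visit but attaches no threshold to it. Randomization and first treatment may take place at that visit or within 4 weeks of it. Baseline titre is not among the prognostic factors that section 3.6 compares by arm.

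**Endpoint.** Sections 3.2 and 3.6 define eradication as anti-FVIII below 0.6 B.U. by CBA by week 48, repeated and confirmed. Neither makes it conditional on an earlier positive result. Section 3.6 compares time to eradication by a piecewise exponential model and does not say how a subject negative at time zero enters it.

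**Contrary wording.** Section 3.6 speaks of becoming inhibitor-free. Section 4.2 says the trial "is limited to male children or adults with severe hemophilia A and an inhibitor to factor VIII". Section 4.1 describes "those who have been refractory or never tolerized at the same HTCs", and the recruitment estimate in section 3.5 reads "Our 2019 survey indicates there are 274 refractory inhibitor patients at 31 HTCs". The summary's Study Population entry and section 3.2 tie entry to ITI status.

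**The concern.** Eradication presupposes an inhibitor. If the entry wording lets in a subject who has none, and the endpoint asks only whether the titre is below 0.6 B.U., he meets the endpoint whatever he receives. The confirmation step does not remove him: someone negative at baseline who stays negative confirms every time.

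Such subjects raise the reported rate in both arms and pull the two rates together. The result would then partly describe people in whom there was nothing to eradicate. With 90 subjects and a design rate of 95% in one arm, there is little room for that.

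**Working it through.** **1. Can the case arise on the text?** Three conditions are needed.
- Entry without a current inhibitor: sections 3.5 and 4.1 accept a past one.
- No check before randomization: a baseline titre is drawn, but no threshold is attached and randomization may happen the same day.
- Endpoint met without change: the definition is an absolute level with confirmation.

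All three hold in the visible text.

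**2. Inputs.** From section 3.6: 95% versus 80% inhibitor-free by week 48, 1:1 allocation, final posterior threshold 97.9%, and at least 80% power at two-sided 5%. From section 3.5: N = 90, so 45 per arm. Assumed, because the documents give no value: *q*, the share negative at baseline who stay negative, equal in both arms, at 5, 10 and 20% (4.5, 9 and 18 of 90). The 95% and 80% are taken to hold for baseline-positive subjects, with constant hazards. The interim look is ignored.

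**3. Reproducing the plan's power.**
- HR = ln(1 − 0.95) / ln(1 − 0.80) = 1.861
- Expected events = 45 × (0.95 + 0.80) = 78.75
- Schoenfeld power = Φ(ln HR × √(events/4) − z)
- ln HR × √(events/4) = 0.6213 × 4.4371 = 2.757
- Two-sided 5%, z = 1.960: Φ(0.797) = 78.7%, close to the stated 80%
- 97.9% threshold, z = 2.0335: Φ(0.723) = 76.5%, the reference below

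**4. Baseline negatives counted as eradications.** Each arm's rate becomes q + (1 − q)p, and the difference becomes (1 − q) × 15 points.

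| q (assumed) | Rates, % | Difference, points | HR | Events | Power, % |
|---|---|---|---|---|---|
| 0 | 95 vs 80 | 15 | 1.861 | 78.75 | 76.5 |
| 5% | 95.25 vs 81.0 | 14.25 | 1.835 | 79.3 | 74.8 |
| 10% | 95.5 vs 82.0 | 13.5 | 1.808 | 79.9 | 73.0 |
| 20% | 96.0 vs 84.0 | 12.0 | 1.756 | 81.0 | 69.2 |

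**5. Baseline negatives left out without replacement.** The rates stay at 95% versus 80% and the HR at 1.861. Events fall to 78.75 × (1 − q) = 74.8, 70.9 and 63.0, and power to 74.3, 72.0 and 66.7%. Leaving them out corrects what is estimated but does not restore power.

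**6. Cross-check.** A Bayesian simulation with the interim look, one hazard piece, near-flat gamma priors and uniform 6-year accrual (the last three assumed) gave 78.0% at q = 0, 74.5% at 10% and 70.0% at 20%, counting such subjects as events at time zero. With four 12-week pieces the starting level was 60.9%. The level depends on the method, so the drops are what to read.

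**7. Type I error.** If both arms share the same p, then q + (1 − q)p is the same in both. Randomization balances q in expectation, so the effect is dilution. Chance imbalance remains possible with 45 per arm.

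**The case against.** The strongest reply is that the trial plainly means to enrol people who have an inhibitor. The contrary wording says so, and the survey count of refractory patients suggests that most recruits will have a persisting titre. A historic peak can also describe when the high value was recorded, not that the inhibitor has gone. The inclusion list in section 4.3 shows only two items with no inhibitor criterion, so it looks incomplete, and the eligibility form mentioned in section 4.4 is not in the documents. All of this stands. It makes *q* probably small and limits any claim of absence to the visible text. It does not supply a titre rule.

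Three stronger readings are tempting and not supported.
- A reader might infer from "or ITI-refractory or ITI-naive" in section 3.5 that a past inhibitor qualifies regardless of ITI status. That sentence also reverses the age limit given elsewhere, and the summary and section 3.2 tie entry to ITI status. It is too weak a basis for a literal reading.
- A reader might infer from "with confirmation on stored aliquots for those testing negative (< 0.6 B.U" in the section 3.2 blood-draw text that negative baselines are expected. This is general laboratory handling, and section 3.3 attaches the stored-aliquot confirmation to positive results instead.
- A reader might carry baseline negatives as at-risk non-events to week 48, which would cut approximate power to 53.3% at q = 5% and 24.0% at 20%. A subject confirmed below 0.6 B.U. meets the plan's own event definition, so the documents do not support counting him as a failure.

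**Conclusion.** The point holds as a gap between the entry wording and the endpoint. On the visible text, a subject with no inhibitor at baseline can be randomized and counted as an eradication. The plan's intent runs the other way, but no operative rule enforces it.

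The size is modest. At q = 5% the difference loses 0.75 points and power about 2 points; at 20% the losses are 3 points and about 7 points. These figures rest on assumed values of *q*, equal shares in the arms, constant hazards and a Schoenfeld approximation. There is no case for type I error inflation. It should be fixed because the remedy uses an assay already drawn and settles who the eradication rate describes.

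**What to change.** 1. **Subjects still to be enrolled.** Require anti-FVIII of 0.6 B.U. or more by CBA on the screening sample, resulted before randomization within the 4-week window that section 3.2 already allows. Bring sections 3.5, 4.1, 4.2 and 4.3 into line. Reconcile the enrollment wording as well: section 3.2 treats a subject as enrolled on signing consent, section 4.4 only once screening assessments are complete, and section 3.4 ties the first dose to 24 hours from enrollment.

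2. **Subjects already randomized.** State in section 3.6, before the interim look, that eradication requires a baseline CBA of 0.6 B.U. or more. Make the primary comparison by assigned arm in all randomized subjects who are positive on the pre-dose baseline sample. This is a pre-randomization characteristic, so the randomized comparison is preserved. Tabulate baseline-negative subjects by arm. Because section 3.2 promises an intention-to-treat analysis, also report all randomized subjects, with baseline negatives counted as events, as a sensitivity analysis.

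3. **Avoid delayed entry.** Do not let a baseline-negative subject join the risk set at a first positive on-study CBA. Turning positive happens after randomization and could differ by arm.

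**Cost.** One inclusion line and a short rule in section 3.6, plus a short wait for the titre. If a share *f* of otherwise eligible patients is baseline-negative, 90/(1 − f) must be screened to reach 90: about 95, 100 and 113 at f = 5, 10 and 20% (assumed). Power is not recovered for baseline-negative subjects already randomized.

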3.6 Statistical Considerations

The purpose of the **Inhibitor Eradication Trial** is to compare novel agents, *Eloctate ITI* with or without *Emicizumab*, in the eradication of inhibitor formation. The results will be compared with hemophilia genotype, trough FVIII chromogenic activity, HLA, and FVIII-specific T cell response by ELISPOT assay from baseline, in order to determine correlation of each assay with inhibitor development over time by descriptive statistics.

Demographic and other baseline characteristics will be summarized using descriptive statistics or counts and percentages, as appropriate. Data to be tabulated will include, but not be limited to, age, race, height, weight, frequency and site of bleeds (hematoma, joint, CNS), emicizumab use, circumcision bleeding and/or treatment, surgery or procedures. All subjects enrolled in the study and who receive *Eloctate ITI* plus *Emicizumab* or *Eloctate ITI alone* will be included in the evaluation for safety. Data on treatment administration and adherence to assigned treatment will be presented. All subjects enrolled in the study and who receive *Eloctate ITI* with/without *Emicizumab* will be included in the evaluation for safety.

Safety measures will include the number and frequency of bleeding events (hematomas, joint, CNS bleeds) during the 48-week study, and the frequency and time to central line infections. Patient diaries will be reviewed monthly for bleeding frequency and site, and for dose and frequency of treatment. If breakthrough bleeds occur, additional treatment will be given at the discretion of the subject's physician, after which treatment may be continued at least weekly or escalated per physician discretion. Subjects will be closely monitored for adverse events, including allergic reactions, thrombosis, bleeding: these events will be summarized over time on study drug. Adverse events will be evaluated for frequency, relatedness, and severity.

Adverse events will be classified using CTCAE System, Vol 4.03, 2010. Tabulations of adverse events by frequency, relatedness, and severity will be presented. Serious adverse events, laboratory parameters, and vital signs will be presented using descriptive statistics for changes over time. Concomitant medications and physical exam data will be summarized over time.

The **Primary Endpoint** is the probability of becoming inhibitor-free by 48 weeks, where the eradication of inhibitor formation is defined as anti-FVIII < 0.6 B.U. by chromogenic Nijmegen Bethesda assay (CBA). We *hypothesize* that tolerance induction with *Eloctate ITI* plus *Emicizumab* is superior to *Eloctate ITI* alone in eradicating inhibitors in children and adults with severe hemophilia A and inhibitors. While both drugs may shorten ITI and even be synergistic, there is equipoise.

Analysis of the Primary Endpoint: We propose to take advantage of prior historical information on inhibitor formation to improve power on the Prevention Trial, and efficient use of inhibitors developing on the Prevention Trial (PRO19040140) to enroll in the Eradication Trial. For the **Eradication Trial**, we propose a Bayesian design and analysis plan to test if *Eloctate* ITI plus *Emicizumab* is superior to *Eloctate ITI* alone. Given the lack of data on either arm, we used two non-informative priors and 1:1 randomization allocation. Non-informative Bayesian priors were used for both arms as there are no published data regarding the time to inhibitor eradication with *Emicizumab* or Eloctate. The time to inhibitor eradication will be compared between the two assigned treatment arms by piecewise exponential survival models to determine the probability of being inhibitor-free at 48 weeks. Monte-Carol Markov-Chains (MCMC) were utilized to determine the posterior probability of the outcome when determining the operating characteristics. At the interim, once 75% of the subjects are randomized, the Bayesian posterior probability that either *Eloctate ITI plus Emicizumab* or *Eloctate ITI alone* is more likely to be inhibitor-free must be at least 99.5% to stop the trial. Assuming the trial did not stop at the interim, then to declare significance at the end of the trial, the Bayesian posterior probability that either arm, *Eloctate ITI*

plus Emicizumab or *Eloctate ITI alone* is more likely to be inhibitor-free at must be 97.9%. This maintains type 1 error at 5%, two-sided, with at least 80% power for superiority if we assume the true condition is that *Eloctate ITI plus Emicizumab* has an inhibitor-free rate of 95% and Eloctate ITI has an inhibitor-free rate of 80%.

Subjects reaching the primary endpoint: The primary endpoint is inhibitor eradication, defined as anti-FVIII < 0.6 B.U., by chromogenic Nijmegen Bethesda assay (CBA). A local lab anti-FVIII < 0.6 B.U. will be repeated on this, or if insufficient, a repeat sample within 7 days, and a second sample obtained within 4 weeks for confirmation. A central lab anti-FVIII < 0.6 B.U. will be repeated within 4 weeks for confirmation. If confirmed, subjects will either continue *Eloctate or rFVIIa* for treatment of bleeds, depending on the inhibitor titer per discretion of the subject' treating physician, but remain on study follow-up through week 48. For clarification, time to peak FVIII >60% will be determined at subsequent testing after confirmation of anti-FVIII < 0.6 B.U. Prognostic factors collected at baseline, including age, race, family history of inhibitors, current or past emicizumab use, and past circumcision, will be compared by treatment arm.

The **Secondary Endpoints** include a) safety measured by the number and frequency of bleeding events (hematoma, joint, CNS bleeds), the frequency and time to central line infections; and the number and frequency of allergic reaction, and thrombosis; and b) mechanism of inhibitor prevention by FVIII-specific T cell ELISPOT (Ig, RNA), performed on an aliquot of PBMCs; and genotype, HLA, and trough chromogenic FVIII drawn on the buffy coat of anti-FVIII plasma samples. ELISPOT assays will be performed on T cell populations depleted of regulatory T cells (T reg) (CD4+CD25+FoxP3+) to determine the role of T regs in controlling immune response to FVIII.

Analysis of Secondary Endpoints: The trial is not powered to analyze secondary endpoints statistically, but will collect these endpoints and perform descriptive statistics and correlations of safety and T cell mechanism by study arm, and with hemophilia genotype, HLA, and antigen-specific (FVIII) T cell responses (ELISPOT) from baseline, in order to determine correlation of each assay with inhibitor development over time by descriptive statistics.

Subjects reaching secondary clinical endpoints: The clinical secondary endpoint will include safety measures, including the number and frequency of bleeding events (hematomas, joint, CNS) during the 48-week study, and the frequency and time to central line infections. Patient diaries will be reviewed monthly for bleeding frequency and site, and for dose and frequency of treatment. If breakthrough bleeds occur, additional treatment will be given at the discretion of the subject's physician, after which treatment may be continued at least weekly or escalated per physician discretion. Subjects will be closely monitored for adverse events, including allergic reactions, thrombosis, bleeding: these events will be summarized over time on study drug. Adverse events will be evaluated for frequency, relatedness, and severity.

